1.1 Purpose

This Primary Statistical Analysis Plan (SAP) describes the primary and key secondary estimands and other secondary outcome measures that will address specific study objectives and interim monitoring of the A5404 study. The Primary SAP includes general analytic approaches for all primary estimands, key secondary estimands, and other outcome measures in the primary manuscript(s) or submitted to ClinicalTrials.gov (regardless of the reporting timeline). The Primary SAP facilitates discussion of the statistical analysis components among the lead study investigators and statisticians, helping them agree on the statistical analyses to be performed and presented in the primary analysis report.

The Analysis Implementation Plan (AIP) provides detailed outlines of tables, figures, and coding descriptions.

A separate SAP will provide outlines of analyses for other objectives and outcome measures not included in the Primary SAP.

1.2 Version History

Summary of Major Changes:

Version 1.0: Not applicable; original version.

Version 2.0: Modifications per LOA #1

- Modifications to the treatment regimens throughout to match revised language in LOA #1.
- Modifications to general language throughout to match revised language in LOA #1.
- Revision to Section 2.5 to reflect updated trigger for first SMC review per LOA #1.
- Modifications throughout to reflect revised time points for outcome measures 3.1.1, 3.2.2, and 3.2.6.
- Modification to Retrospective Safety Set to allow for inclusion of participants who received both doses of vaccine prior to study entry.

Version 3.0: Modifications in anticipation of reduced sample size for the final analysis and modifications to align with CM #1.

- Revised naming of mRNA vaccination regimens (to align with CM #1)
- Modifications to text to clarify initially intended analyses and introduce revised plans in the event of reduced final sample size
 - Primary analyses will no longer focus within each select therapy group. Active therapies will be combined together into a single group.
 - Remove references to “active comparator” group since no participants enrolled from an active comparator in ACTIV-2/A5401

- Focus will be on descriptive analyses among participants who received active therapies in ACTIV-2/A5401, those who received placebo, those who received Camostat or placebo.
- Revised language to state that formal comparisons between groups may not be justified due to small sample size.
- Removal of Retrospective Safety Analysis Set (no longer relevant).
- Revisions to Report Contents corresponding to changes throughout.
- Revisions to remove secondary objectives and corresponding outcome measures according to CM #1.

NOTE: SAP version 3.0 aligns with protocol version 2.0 plus CM #1. At the time of this SAP version finalization (January 17, 2023), CM #1 has not yet been released to sites for implementation. The A5404 protocol v2.0 was under revision since September 2021. The team have faced a number of decisions that changed the course of action on multiple occasions for how best to proceed with changes to the protocol. The SAP was updated (in draft state) concurrent with all protocol revisions. The final analysis report for A5404 was conducted under this SAP version 3.0. The analyses align with protocol version 2.0/CM #1.

Version 3.1: Minor revision to indicate that CM #1 was distributed to sites on January 25, 2023.

2 Study Overview

2.1 Study Design

A5404 is a phase IV, open-label, sub-study of ACTIV-2/A5401 aiming to evaluate how prior investigational therapy for COVID-19 versus comparator (placebo or active comparator) affects vaccine response. This is a non-randomized study designed to have reasonable precision to estimate the difference in immune response between those with versus without prior select investigational therapy for COVID-19. Results will be interpreted in the context of available information from outside the study when analyses are completed.

The study will enroll a target of 70 participants from each ACTIV-2/A5401 select therapy group (comprised of individuals exposed to active treatment and individuals exposed to the corresponding placebo or active comparator). In addition, up to 70 individuals without prior history of SARS-CoV-2 infection will be enrolled based on vaccine supply at each A5404 site. The total sample size will depend on how many therapies are selected from ACTIV-2/A5401. The ratio of participants with active therapy exposure versus corresponding comparator exposure in ACTIV-2/A5401 is also unknown a priori, as the randomization ratio for ACTIV-2/A5401 study depends on the number of agents concurrently enrolling. If the target sample of 70 participants for a select therapy group is not able to be met from Phase II participants in the ACTIV-2/A5401 trial, then enrollment will open to participants from the respective Phase III group in ACTIV-2/A5401.

Eligible participants will receive mRNA COVID-19 vaccine in one of three ways:

Cohort 1: ACTIV-2/A5401 participants

Participants will receive one of the following regimens:

Cohort 1a: Moderna mRNA-1273 COVID-19 vaccine, 100 µg (0.5 mL) to be administered intramuscularly (IM) at Entry and Day 28. Both doses will be provided by the study.

Or

Cohort 1b: Participants will receive a two-dose series of a community-provided mRNA-based COVID-19 vaccine that has received FDA EUA or FDA approval (e.g., Moderna or Pfizer). Vaccine will not be provided by the study.

NOTE: These participants may enter the study before their first vaccine dose, after their first vaccine dose, or after their second vaccine dose.

Or

Cohort 1c: Participants will receive their first Moderna mRNA-1273 COVID-19 vaccine dose in the community. Their second Moderna mRNA-1273 dose will be provided by the study (100 µg [0.5 mL] to be administered IM 28 days after their first dose).

NOTE: These participants may enter the study before or after their first vaccine dose.

Or

Cohort 2: Participants without prior history of SARS-CoV-2 infection

Participants will receive the following study-provided regimen: Moderna mRNA-1273 COVID-19 vaccine, 100 µg (0.5 mL) to be administered IM at Entry and Day 28.

All participants will have blood collected and immune responses measured before the first vaccine dose (if feasible), and before the second dose of vaccine (e.g., 28 days later for Moderna vaccine and 21 days later for Pfizer vaccine if given in the community) (if feasible), and 56 (if feasible), 140, 365, and 730 days after their first vaccine dose.

We initially intended to conduct the primary analysis separately within each select ACTIV-2/A5401 therapy group. However, due to a lower than anticipated accrual, we revised the plan to instead conduct the primary analysis combining participants from select ACTIV-2/A5401 therapy groups. The primary analysis will occur after the last enrolled participant from ACTIV-2/A5401 has reached the Day 140 study visit.

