56 and 140 Days Post-Vaccination #1 for ACTIV-2/A5401 Participants Who Received First and Second Doses of a Community-Provided mRNA-based COVID-19 Vaccine before Entry

- **56 days post-vaccination #1 timepoint:**
 - This visit will not be conducted if the participant enrolls more than 56 days after their first vaccine dose.
 - This visit may be combined with the Entry visit if the participant enrolls between 56 and 63 days after their first mRNA COVID-19 vaccine dose. Evaluations indicated at both timepoints will be conducted only once.
- **140 days post-vaccination #1 timepoint:** This visit may be combined with the Entry visit if the participant enrolls between 133 and 147 days after their first mRNA COVID-19 vaccine dose. Evaluations indicated at both timepoints will be conducted only once.

k. Section 6.3.7 Vaccine Administration

The first sub-section title was changed to, “Documentation of Community-Provided COVID-19 Vaccination”

l. Section 6.3.8 Vaccine Symptom Screen

The first sentence has been revised to, “For participants who receive community-provided mRNA-based COVID-19 vaccine: If the participant enrolls >14 days after the first or second dose of their vaccine, then a Vaccine Symptom Screen is not collected for the doses provided prior to enrollment.”

4. Section 4.1, Inclusion Criterion 4.1.3:

The following note was added.

NOTES:

- Selected investigational therapies will be posted on the A5404 PSWP.
- **For participants who received camostat or the active comparator/placebo for camostat: Receipt of ≥50% of the doses indicated in ACTIV-2/A5401.**

5. Section 5.2, Study Product Formulation and Preparation**a. In section 5.2.1 Formulation and Storage, the following modifications have been made:**

The Moderna mRNA-1273 COVID-19 vaccine is supplied as a frozen suspension, stored between ~~-25-50°~~ to -15°C, in multi-dose vials, and does not contain a preservative. ~~Store in the original carton to p~~ **Protect** from light. Do not store on dry ice or below ~~-40-50°C~~. The Moderna mRNA-1273 COVID-19 vaccine is white to off-white suspension. It may contain white or translucent product-related particulates.

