2.4 Overview of Sample Size Considerations

The study is descriptive and designed to have reasonable precision around the primary outcome measure estimate. See Section 10.4 of the study protocol (version 2.0) and CM #1 for additional details. In January 2022, the study team noted that the observed enrollment into the study was lower than anticipated and that achieving the target sample size of 70 participants per select therapy group was unlikely. The study closed to accrual on February 25, 2022, and enrolled a total of 43 participants with no enrollment of participants exposed to active comparator in ACTIV-2/A5401. Therefore, we have revised the analyses as necessary and stated alternatives for use with small sample sizes.

For the first primary outcome measure (NAb levels 140 days after the first vaccine dose, see SAP Section 3.1.1), we will estimate the NAb levels 140 days after the first vaccine dose in each of the following groups:

- (1) Participants exposed to AZD7442 IM or IV, BRII-196+BRII 198 IV, SAB 185 (3,840 or 10,240 units/kg), BMS 096414+BMS 986413 subcutaneous in ACTIV-2/A5401
- (2) Participants exposed to placebo in ACTIV-2/A5401
- (3) Participants exposed to placebo or Camostat Oral in ACTIV-2/A5401

We will also estimate the ratio of geometric mean responses (GMRs) for participants with COVID-19 therapy exposure (group 1 above) versus participants who received placebo (group 2 above). The precision on this estimate may be low due to limited sample size. A ratio of GMRs (GMR for select therapy exposed divided by GMR for placebo) of 1 indicates no difference in NAb response. A ratio less than 1 indicates lower NAb response among those who received COVID-

19 investigational therapy exposure compared to those who received placebo. In a sensitivity analysis we will consider a comparison of group 1 versus group 3.

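### The pooled NAb ratio sets four non-Camostat therapies against all placebo recipients, with no allowance for parent therapy group or enrolment period, so it could be biased by an unknown amount

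*SAP*

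**What the plan says.** SAP section 2.1 records the change of plan: "We initially intended to conduct the primary analysis separately within each select ACTIV-2/A5401 therapy group", and then, because of low accrual, "we revised the plan to instead conduct the primary analysis combining participants from select ACTIV-2/A5401 therapy groups". Section 1.2 puts it as "Active therapies will be combined together into a single group".

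Section 2.4, repeated in 5.1, 5.2, 7.7 and 7.8, defines the two sides of the main contrast:
- Group 1: "1) Participants exposed to AZD7442 IM or IV, BRII-196+BRII 198 IV, SAB 185 (3,840 or 10,240 units/kg), BMS 096414+BMS 986413 subcutaneous in ACTIV-2/A5401". Camostat is not listed.
- Group 2: "Participants exposed to placebo in ACTIV-2/A5401", with no limit to placebo for the group 1 agents.

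Camostat is a selected therapy. Letter of Amendment #1, item 4, adds a dosing note to inclusion criterion 4.1.3 that begins "For participants who received camostat or the active comparator/placebo for camostat", so placebo recipients for Camostat are eligible.

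Section 4 of the SAP specifies linear regression of log10 NAb on a single indicator of therapy versus placebo. On allocation, section 2.1 says the active-to-comparator ratio is not known in advance, since "the randomization ratio for ACTIV-2/A5401 study depends on the number of agents concurrently enrolling".

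Three planned analyses come near the issue:
- a repeat of group 1 against group 3 (placebo or Camostat);
- an optional analysis adjusted for time from therapy to first vaccine dose;
- for the primary estimand only, subgroups by vaccine brand.

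The last two depend on numbers.

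**The concern.** Under the initial plan, active recipients were compared with the placebo recipients of their own therapy group, who shared the same agents on offer and the same period of enrolment. The pooled contrast gives that up. If the mix of parent groups or periods differs between the active and placebo sides, any difference in NAb level between those groups or periods enters the ratio and looks like an effect of therapy. Participants enrolled as placebo for Camostat would be the extreme case, because they have no active counterpart in group 1.

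The SAP's own statement of the objective in 5.1 takes placebo for the investigational therapy as the comparator, and group 2 as worded is wider than that. The ratio and its 95% interval are the study's main result. The interval reflects sampling error only, so it would not signal a shift of this kind. The key secondary estimand in 5.2 uses the same groups. The safety analysis in 5.3 counts Camostat as active, so the Camostat mismatch does not arise there, although it too makes no allowance for parent group.

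**Working it through.** **The plan's own precision.** Inputs from SAP section 2.4: SD 0.5 on the log10 scale, 35 versus 35. Interval = 10^(±t × 0.5 × √(2/35)), with 68 df.
- 90%: (0.63, 1.58). 95%: (0.58, 1.73). Both match the SAP.
- At the smaller totals the SAP mentions, split 1:1, the standard error is 0.5 × √(2/10) = 0.224 at n = 20 and 0.5 × √(2/15) = 0.183 at n = 30. The 95% limits are the estimate divided and multiplied by 2.95 and 2.37 respectively.

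**Formula for the bias.** If no therapy changes the response in any parent group, the expected pooled difference in log10 NAb is the sum over parent groups of (share among actives − share among placebos) × parent-group mean. It is zero if the shares are equal or the means are equal. For the key secondary estimand, read mean log10 fold change in place of mean level.

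**Illustration A: unequal allocation.** Assumed: two parent groups of equal size, one allocated 1:1, the other (B) more heavily to active, and B's mean higher by 0.3 log10. The documents give neither the ratios nor the gap.

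| Allocation in B | B's share of actives | B's share of placebos | 0.3 × difference | Spurious ratio |
|---|---|---|---|---|
| 1:1 | 0.50 | 0.50 | 0 | 1.00 |
| 2:1 | 0.57 | 0.40 | 0.051 | 1.13 |
| 3:1 | 0.60 | 0.33 | 0.080 | 1.20 |
| 4:1 | 0.62 | 0.29 | 0.099 | 1.26 |

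With a 0.5 log10 gap the last three become 1.22, 1.36 and 1.46. If B's mean were lower, each ratio would be inverted.

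**Illustration B: Camostat placebos in group 2.** Assumed: they form a share s of group 2 and differ from the rest by 0.3 log10. Ratio = 10^(±0.3 × s).
- s = 25%: 10^(±0.075) = 0.84 or 1.19.
- s = 50%: 10^(±0.15) = 0.71 or 1.41.

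**Against random error.** The shifts in A at the 0.3 gap are 0.051 to 0.099 log10. That is 0.23 to 0.44 standard errors at n = 20 and 0.28 to 0.54 at n = 30.

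**Would a parent-group term help?** A null simulation (4,000 runs, SD 0.5, n = 33) assumed group A with 8 active and 8 placebo, group B with 9 and 3, and 5 Camostat placebos. B's mean was set at +d and the Camostat mean at −d relative to A, so the two routes add up.
- Single indicator: the ratio averaged 1.17, 1.35 and 1.56 at d = 0.1, 0.2 and 0.3, with 95% interval coverage of 94%, 90% and 85%.
- Same model plus parent-group terms: ratio 0.99 to 1.01, coverage about 95%.
- With the sample doubled to 66 and d = 0.3, the single-indicator ratio stayed at 1.57 and coverage fell to 70%. A larger study would not remove the bias.

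**The case against.** The strongest reply is that the SAP already restrains the inference. It calls the study non-randomized and descriptive, says formal comparisons may not be justified, warns of limited interpretation at n = 20 or 30, and openly explains that accrual forced the pooling. Only 43 participants enrolled in all, so stratification may be very imprecise. This stands as a reason to leave the pooled analysis as the primary one. It does not cover the point, because the warnings concern precision and this is a possible bias in the estimate itself.

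Four stronger readings are tempting, and the documents do not support them.
- A reader might infer that allocation ratios did vary among A5404 enrollees. Section 2.1 says only that the ratio is unknown in advance and depends on concurrent agents.
- A reader might infer that Camostat placebos are certainly in group 2. They are eligible and the wording admits them, but no count is given. Nor do the documents say whether placebo recipients belonged to one agent or were shared across agents.
- Mirror-image ratios of 3:1 and 1:3 with a 0.3 gap would give 10^(0.3 × 0.5) = 1.41. Nothing suggests that any therapy group had more placebo than active.
- It would be wrong to say that nothing planned touches the issue. The time-to-vaccine adjustment and the brand subgroups bear on two plausible reasons for group differences. They are conditional and partial: two participants with equal intervals may still come from different parent groups or periods.

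The group 1 versus group 3 repeat does not help, since it keeps the whole placebo pool and adds Camostat recipients to it. Section 7 promises summaries by select therapy group, but its parenthesis reads as active, placebo or the three pooled groups, and 7.7 and 7.8 list no within-group contrast.

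**Conclusion.** The point holds as a possible bias, not a demonstrated one. The pooled primary and key secondary ratios no longer compare active recipients with their corresponding placebo, and no planned analysis restores that comparison.

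A bias needs two things: a different mix of parent groups or periods on the two sides, and NAb differences between those groups or periods. The documents neither show nor exclude either, so size and direction are unknown. Under the moderate assumptions above the ratio moves by a factor of about 1.13 to 1.26 through allocation, or to 0.84 or 1.19 through Camostat placebos. Either is well inside the 95% limits expected at n = 20 to 30. It deserves a sensitivity analysis because it is systematic, the interval does not reflect it, and the check is cheap.

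**What to change.** Keep the pooled analysis as it is. In SAP sections 5.1, 5.2, 7.7 and 7.8:

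- Report counts by parent therapy group and arm. Section 7.2 already plans accrual by select therapy group, so the variable appears to be available.
- Add sensitivity analysis (a): group 1 against only those placebo recipients who correspond to, or were randomized concurrently with, the group 1 agents.
- Add sensitivity analysis (b), if numbers permit: the same regression with a term for parent therapy group. If placebo was shared across agents, use the set of concurrently available agents or the enrolment period instead.
- If (b) cannot be fitted, state that the pooled ratio is not protected by the parent randomization.

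Section 1.2 says the final report was conducted under version 3.0, so analyses added after that report should be labelled post hoc. Because entry to A5404 was itself not randomized, (a) and (b) bring the comparison closer to the parent randomization without fully restoring it.

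The cost is a table and two model runs on existing data. Analysis (a) has fewer placebo participants. Analysis (b) loses about 3 degrees of freedom with four parent groups, or 4 if Camostat placebos stay in as a fifth, and a group with only one arm adds nothing to the contrast. Intervals widen in the sensitivity analyses only.

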2.2 Hypotheses

This study hypothesizes that there may be differences in immune response following mRNA-based vaccination for SARS-CoV-2 among individuals with prior SARS-CoV-2 infection between those exposed to prior select therapies versus those who received a placebo. This study focuses on descriptive objectives rather than formal statistical hypothesis testing.

2.3 Study Objectives

This Primary SAP addresses the following primary and secondary objectives listed in the study protocol. Other study objectives in the protocol will be addressed in subsequent analysis plans.

The primary and secondary study objectives below will be analyzed descriptively and conducted only if sample size permits. The primary objective analysis will be conducted once the last enrolled participant for that group has completed the Day 140 study visit and all associated queries have been resolved. Analysis of the secondary objective will occur at the same time.

Note: In CM #1, four of the originally stated secondary objectives were relegated to exploratory/other objectives due to low enrollment.

2.3.1 Primary Objective

To estimate the difference in neutralizing antibody (NAb) response to mRNA-based COVID-19 vaccine among participants with prior SARS-CoV-2 infection who received investigational therapy exposure compared to participants without prior investigational therapy exposure (placebo for investigational therapy or active comparator).

2.3.2 Secondary Objective

To explore the safety of mRNA-based COVID-19 vaccines among participants with prior COVID-19 who received investigational therapy or its comparator for COVID-19 and persons who are SARS-CoV-2 naïve.

2.4 Overview of Sample Size Considerations

The study is descriptive and designed to have reasonable precision around the primary outcome measure estimate. See Section 10.4 of the study protocol (version 2.0) and CM #1 for additional details. In January 2022, the study team noted that the observed enrollment into the study was lower than anticipated and that achieving the target sample size of 70 participants per select therapy group was unlikely. The study closed to accrual on February 25, 2022, and enrolled a total of 43 participants with no enrollment of participants exposed to active comparator in ACTIV-2/A5401. Therefore, we have revised the analyses as necessary and stated alternatives for use with small sample sizes.

For the first primary outcome measure (NAb levels 140 days after the first vaccine dose, see SAP Section 3.1.1), we will estimate the NAb levels 140 days after the first vaccine dose in each of the following groups:

- (1) Participants exposed to AZD7442 IM or IV, BRII-196+BRII 198 IV, SAB 185 (3,840 or 10,240 units/kg), BMS 096414+BMS 986413 subcutaneous in ACTIV-2/A5401
- (2) Participants exposed to placebo in ACTIV-2/A5401
- (3) Participants exposed to placebo or Camostat Oral in ACTIV-2/A5401

We will also estimate the ratio of geometric mean responses (GMRs) for participants with COVID-19 therapy exposure (group 1 above) versus participants who received placebo (group 2 above). The precision on this estimate may be low due to limited sample size. A ratio of GMRs (GMR for select therapy exposed divided by GMR for placebo) of 1 indicates no difference in NAb response. A ratio less than 1 indicates lower NAb response among those who received COVID-

19 investigational therapy exposure compared to those who received placebo. In a sensitivity analysis we will consider a comparison of group 1 versus group 3.

A sample size of 70 participants gives reasonable anticipated precision for the ratio of GMRs. For a standard deviation of 0.5 and a sample size of 70 participants who receive vaccine (a 1:1 ratio; 35 with prior select therapy and 35 who received placebo), the 90% confidence interval for the ratio of GMRs is (0.63, 1.58) and the 95% confidence interval is (0.58, 1.73). These confidence intervals suggest reasonable precision to rule out reductions in response associated with prior select therapy of about 40% or more, or increases of about 60% or more. However, with sample sizes of 20 or 30, we anticipate wide confidence intervals (low precision) and therefore limited interpretation.

The anticipated precision for the estimate of the key secondary outcome measure, the relative change in NAb level pre-vaccine to post-vaccine (see SAP Section 3.2.1), is also reasonable for a sample size of 70. Assuming a variability of changes in NAb level of SD=0.4, a sample size of 70 participants receiving vaccine with equal numbers with versus without prior investigational therapy, the 90% confidence interval is (0.69, 1.44) and the 95% confidence interval is (0.64, 1.55) when the observed ratio of GMRs comparing participants with versus without prior select therapy is 1. However, with sample sizes of 20 or 30, we anticipate wide confidence intervals (low precision) and therefore limited interpretation.

